#### 7.1.2 Adverse Events with Treatment Relatedness

TEAE relatedness to SM will be summarized based on derived binary values as: "Drug Related" if the relationship to SM is probably or related or "Not Related" if the relationship to SM is not related or unlikely related.

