5.1.1 Inclusion Criteria

The following inclusion criteria must be met in order for a subject to be enrolled and randomized to treatment:

1. Healthy male or female subjects, age 12-17 years at the time of screening, including outpatients in foster care living at home.

- 2. Diagnosis of ADHD according to the *Diagnostic and Statistical Manual of Mental Disorders-5* (DSM-5) confirmed by MINI-KID.
- 3. Monotherapy treatment with an FDA-approved optimized ADHD medication (psychostimulants and non-stimulants for at least one month prior to Screening and willing to maintain the dose throughout the duration of the study.
- Retrospective Modified Overt Aggression Scale (R-MOAS) score of ≥ 20 at Screening and Visit 3.
- 5. CGI-S score at least moderately ill (\geq 4) at Screening and Visit 3.
- 6. Vitiello Aggression Questionnaire score from -2 to -5 at Screening.
- 7. Free of antipsychotic medication for at least 2 weeks or 5x drug's half-life or whatever is longer prior to Visit 2.
- 8. Discontinuation of α 2-adrenergic agonists (e.g. clonidine and guanfacine) used for any other reason except for monotherapy treatment of ADHD (e.g. aggression or insomnia) at least two-weeks prior to Visit 2.
- 9. Medically healthy with clinically normal laboratory profiles, vital signs and electrocardiograms (ECGs).
- 10. Able and willing to swallow tablets whole and not chewed, cut or crushed.
- 11. Written informed consent/assent obtained from the subject's parent or legal authorized representative (LAR), and written informed assent from the subject if required.
- 12. Compliance \geq 70% for completion of the IA Diary during the Baseline period.
- 13. IA score \geq 6 during the Baseline period.

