6.4.2.1 Causality

AEs may be categorized as either Adverse Drug Reactions or Suspected Adverse Drug Reactions based on their relationship to SM and the degree of certainty about causality.

- **Suspected adverse drug reactions** (SADRs) are a subset of adverse events for which there is evidence to suggest a causal relationship between the drug and the AE, i.e., there is a reasonable possibility that the drug caused the adverse event.
- Adverse drug reactions (ADRs) are a subset of all SADRs for which there is reason to conclude that the drug caused the event.

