An increase in the CSSRS, Simpson Angus Scale, Barnes Akathisia Scale, or the AIMS will not necessarily be rated as an AE unless the event meets AE criteria.

The Investigator is responsible for evaluating AEs and determining the following:

- Serious vs. Non-serious: Is the event a Serious Adverse Event (SAE)?
- **Causality:** Was AE related or possibly related to the SM?
- Severity: How pronounced is the incapacity/discomfort caused by an AE?

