6.4.2.4 Criteria for Assessing Causality

The Investigator is responsible for determining the relationship between the administration of SM and the occurrence of an AE as **not suspected** or as a **suspected** reaction to SM. These are defined as follows:

Not suspected: The temporal relationship of the AE to SM administration makes a **causal relationship unlikely**, or other drugs, therapeutic interventions, or underlying conditions provide a sufficient explanation for the observed event.

- Not related: Temporal relationship to SM administration is missing or implausible, or there is an evident other cause.
- **Unlikely related**: Temporal relationship to SM administration makes a causal relationship improbable; and other drugs, chemicals, or underlying disease provide plausible explanations.

Suspected: The temporal relationship of the AE to SM administration makes a **causal relationship possible**, and other drugs, therapeutic interventions, or underlying conditions do not provide a sufficient explanation for the observed event.

- **Possibly related:** Temporal relationship to SM administration is plausible, but concurrent disease or other drugs or chemicals could also explain event. Information on drug withdrawal may be lacking or unclear. This will be reported as a **Suspected Adverse Drug Reaction (SADR)**.
- **Definitely related:** Temporal relationship to SM administration is plausible, and concurrent disease or other drugs or chemicals cannot explain event. The response to withdrawal of the medication (dechallenge) should be clinically plausible. The event must be definitive pharmacologically or phenomenologically, using a satisfactory rechallenge procedure if necessary. This will be reported as an **Adverse Drug Reaction** (ADR).

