9.5.1 Adverse Events

AEs will be classified into standardized medical terminology from the verbatim description (Investigator term) using the Medical Dictionary for Regulatory Activities (MedDRA). AEs will be summarized using discrete summaries at the subject and event level by system organ class and preferred term for each group of doses. Similarly, treatment-emergent AEs will be summarized by severity and relationship separately. Verbatim description and all MedDRA level terms, including the lower level terms, for all AEs will be contained in the subject data listings.

All AEs occurring throughout the study period will be recorded. Treatment-emergent AEs (TEAEs) will be collected starting after the first dose of study medication (after Visit 3) to the end of the study. These AEs include those that emerge during treatment or worsen in severity during treatment. These AEs will be tabulated, listed, and analyzed.

Separate TEAE incidence tables will be presented for the two treatment groups. The incidence rates for all SADRs will also be summarized as described for all TEAEs.

In addition, these same tables will be presented by treatment period (Titration, Maintenance, and combined Titration and Maintenance). For the combined Titration and Maintenance Periods, the incidence of TEAEs will also be presented by highest severity reported and the dose of SM at first occurrence. Listings (and tabular summaries, if warranted) of deaths, other SAEs, and other significant TEAEs, including TEAEs resulting in treatment discontinuation, will be provided.

9.5.2 **C-SSRS**

C-SSRS outcomes will be summarized using number and percent of subjects by categories for suicidal ideation only, suicidal behavior only and suicidality (ideation and behavior combined). The summary will be presented by treatment group. The proportion of subjects in each treatment group will be compared with the proportion of subjects in the placebo group using Fisher's exact test or Chi-square test as applicable if appropriate.

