## **5.7** Handling of Missing Data

There will be no substitutions made for missing data points. The number of missing values will be presented in the analysis tabulations, as applicable, but without a percentage.

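### SAP 7.1.2 builds its Drug Related category from a *probably* rating the protocol does not have, and leaves *Possibly related* events unassigned

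*SAP*

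**What the plan says.** SAP 7.1.2 summarises relatedness of treatment-emergent events through a derived two-value variable. Drug Related applies "if the relationship to SM is probably or related"; Not Related applies to events rated not related or unlikely related. No third category is provided.

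Protocol 6.4.2.4 defines the ratings that the investigator assigns. Two sit under Not suspected: *Not related* and *Unlikely related*. Two sit under Suspected:

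- *Possibly related*, reported as a suspected adverse drug reaction (SADR): "Temporal relationship to SM administration is plausible, but concurrent disease or other drugs or chemicals could also explain event".
- *Definitely related*, reported as an adverse drug reaction (ADR): "Temporal relationship to SM administration is plausible, and concurrent disease or other drugs or chemicals cannot explain event".

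Three other protocol passages bear on the intended split. Section 6.4.2.2 puts the causality question as "Was AE related or possibly related to the SM". Section 6.4.2.1 defines SADRs as events where "there is a reasonable possibility that the drug caused the adverse event" and makes ADRs a subset of them. Section 9.5.1 states: "The incidence rates for all SADRs will also be summarized as described for all TEAEs". Protocol 8.1 lets the SAP override the protocol's statistical methods.

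**The concern.** The Drug Related rule uses two labels, and neither is a protocol rating. *Probably* has no counterpart at all. Bare *related* presumably means *Definitely related*, but the SAP does not say so. *Possibly related*, one of the two ratings that make an event suspected, is not named on either side of a variable that is meant to have only two values.

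Because the SAP takes precedence for analysis, a programmer who follows it has a rule with a gap, and no other SAP section fills it. Followed to the letter, with *related* read as *Definitely related*, the Drug Related category shrinks from all suspected reactions to the ADR subset, and the summary understates suspected drug-related events. No other SAP section mentions relatedness, so no other specified table would make up the difference.

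**Working it through.** The plan states no figure to reproduce. The check matches each of the four ratings in protocol 6.4.2.4 against the two SAP categories under three readings of the rule.

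- **A, intended:** *probably* is a slip for *possibly*, and *related* means *Definitely related*.
- **B, as written but with *related* read as *Definitely related*.**
- **C, exact label match** for both Drug Related terms.

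| Protocol rating | Protocol class | A | B | C |
|---|---|---|---|---|
| *Not related* | Not suspected | Not Related | Not Related | Not Related |
| *Unlikely related* | Not suspected | Not Related | Not Related | Not Related |
| *Possibly related* | Suspected (SADR) | Drug Related | none | none |
| *Definitely related* | Suspected (ADR) | Drug Related | Drug Related | none |
| Ratings placed | | 4 of 4 | 3 of 4 | 2 of 4 |

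Under A the result matches the protocol's suspected / not suspected split exactly. Under C the Drug Related category would be empty, which is unlikely to go unnoticed. Reading B is the one that could pass unseen.

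**Size under B.** Let *P* and *D* be the numbers of treatment-emergent events rated *Possibly related* and *Definitely related*.

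- Suspected events that should be counted: *P* + *D*.
- Suspected events counted: *D*.
- Proportion missed: *p* = *P* / (*P* + *D*).

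The value of *p* can lie anywhere from 0 (nothing missed) to 1 (everything missed), and the documents do not narrow it. For subject counts, the proportion missed is the share of subjects with at least one suspected event who have no *Definitely related* event.

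**Which reading is intended.** The variable is two-valued and its Not Related side is complete, so the Drug Related side should hold the remaining two ratings. Protocol 6.4.2.2 pairs *related* with *possibly related*, using bare *related* for the stronger level. Protocol 6.4.2.1 and 9.5.1 treat SADRs as the class to summarise, and that class contains both suspected ratings. All of this points to A.

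**The case against.** The strongest reply is that this is an obvious typing slip. A two-value rule whose other side is fully listed makes the gap hard to miss, and harm requires a programmer to code a label that does not exist, leave a rating unassigned, and have nobody notice. That is fair, and it is why the point is minor. It does not remove the need to correct the rule, because the right reading has to be inferred from a different document.

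Second, the categories must match the eCRF, which is not in the documents. The SAP was finalised after the study was halted, so its labels might reflect the options actually collected. If so, the mismatch lies between the eCRF and the protocol, and SAP 7.1.2 could be correct. This stands: only the label mismatch between SAP and protocol is certain, and any effect on results is conditional.

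Third, one might argue that *p* is unlikely to be negligible, because inclusion criterion 3 requires "Monotherapy treatment with an FDA-approved optimized ADHD medication" and *Definitely related* requires that other drugs cannot explain the event. The argument is weak. Other drugs as a plausible explanation are also part of the definition of *Unlikely related*, and the ADHD drug must have been taken for at least a month before Screening with its dose then held, so it is a less natural explanation for a new event. Nothing here rests on it.

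Fourth, SAP 5.1 and 7.1.5 plan listings, so individual ratings should be recoverable. That limits the harm, although the summary table is what a reader would normally use.

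**Conclusion.** The concern holds. The Drug Related labels in SAP 7.1.2 do not match the causality ratings in protocol 6.4.2.4, and *Possibly related* is assigned to neither category. If the slip is recognised, there is no effect. If the rule is programmed as written, with *related* taken as *Definitely related*, one of the four ratings is left out and suspected events are understated by *p*, which is unknown.

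The point is minor. It touches one descriptive summary, with no hypothesis test or decision rule, in a study whose analysis was cut back after it was halted. The other adverse event outputs (SAP 7.1.1 and 7.1.3 to 7.1.5) are not described as depending on relatedness, although the contents of the overview in 7.1.1 are not itemised. The absence of a separate SADR table is not counted as an error here. Confidence is high for the label mismatch only.

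**What to change.** First check the causality options on the eCRF.

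- If they are the four in protocol 6.4.2.4, reword SAP 7.1.2 along these lines: *Drug Related (Suspected) = Possibly related or Definitely related; Not Related (Not suspected) = Not related or Unlikely related.*
- If the eCRF does offer a *probably* option, reconcile it with protocol 6.4.2.4 and place every option in exactly one category.

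Show missing ratings as a count, as SAP 5.7 already provides: "The number of missing values will be presented in the analysis tabulations, as applicable, but without a percentage".

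The cost is one eCRF check, one SAP sentence and one line of derivation code. No new data are needed.

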#### 7.1.3 Serious Adverse Events

The incidences of SAEs will be presented by SOC and preferred term, and a listing of all SAEs will be presented.

### 7.1.4 Adverse Events Leading to Study Drug Discontinuations

The incidences of TEAEs leading to study drug discontinuation will be presented in listings by SOC and preferred term.

## 7.1.5 Adverse Events of Special Interest

Treatment-emerging EPS (e.g., akathisia, dystonia, Parkinsonism, tardive dyskinesia) and neuroleptic malignant syndrome are reported to the Drug Safety Contact person(s) by completing the Adverse Event of Special Interest (AESI) eCRF in EDC.

The AESIs will be presented by SOC and preferred term.

Subject listings of AEs will be presented.

## **7.2** Clinical Laboratory Tests

The absolute value and change from baseline to EOS for laboratory tests will be summarized using descriptive statistics (n, mean, standard deviation, median, minimum, and maximum) by Treatment groups, laboratory category (Chemistry, Hematology, Immunochemistry, and Urinalysis). The summary will be presented by Treatment group in for Chemistry, Hematology, Immunochemistry and Urinalysis respectively. Subject listings of clinical laboratory data will be presented.

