4.3.2 Treatment Phase: (2-5 weeks)

4.3.2.1 Titration period (2 weeks), Day 1 to Day 14

Inclusion/exclusion criteria will be re-assessed to verify eligibility prior to study randomization at the end of Visit 3. Eligible subjects will be randomized at Visit 3 (Day 1) in a 1: 1 ratio to receive 36 mg/day SPN-810 or placebo and proceed to the two-week Titration period in order to reach the maintenance dose of 36 mg/day over a period of 2 weeks.

4.3.2.2 Flexible Maintenance period (3 weeks), Day 15 to Day 35

Following dose titration, all subjects will remain at the reached dose of SPN-810 (36 mg/day) or placebo on the first week of the Maintenance period. After the first week, the Investigator will clinically assess whether to increase the dose to 45 mg/day SPN-810 or placebo, or remain at 36 mg/day of SPN-810 or placebo. On the following week, the Investigator will re-assess the dosage: the subject may remain at 36 mg/day or 45 mg/day or matching placebo (depending on the dosage from the previous week) or titrate up to the higher dose of 45 mg/day or 54 mg/day of SPN-810 or placebo, respectively. Dose reduction will also be allowed during the second week of the Maintenance period in consultation with the Medical Monitor and the Sponsor; at Visit 6 the Investigator may adjust the dose based upon tolerability.

4.3.3 Conversion Phase (10 days), Day 36 to day 45

At the end of the 3-week Maintenance period (Visit 7), subjects will enter a 10 day Conversion Phase if the subject chooses to enroll into an ongoing open-label extension (OLE) study (i.e., 810P304). A blinded double-dummy conversion card will be distributed to down or up-titrate

This document is confidential. It contains proprietary information of Supernus[®] Pharmaceuticals, Inc. Any viewing or disclosure of such information that is not authorized in writing by the Sponsor is strictly prohibited. Such information may be used solely for the purpose of reviewing or performing this study.

CONFIDENTIAL Version 3

the study medication and matching placebo. Subjects will return to the study site for a final end-of-study (EOS) visit, (Visit 8), after completing the Conversion Phase (Figure 1).

4.3.4 Taper Phase (10 days), Day 36 to day 45

At Visit 7, subjects who opt to discontinue from the study will receive a blinded taper card to titrate down the study medication. At the completion of the Taper Phase, subjects will return to the study site to complete the EOS procedures (Figure 2).

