Subjects who choose to continue into the OLE, will enter the study at a dose of 36 mg/day SPN-810. A subject who discontinues early in the Maintenance period, i.e., prior to Visit 7 may be allowed to participate in the OLE on a case-by-case basis after consultation between the Investigator, Medical Monitor, and the Sponsor.

4.3.5 End of the Study (EOS)/Early Termination, Day 46

Subjects will return to the study site for a final visit, after completing the 10 day period of Taper or Conversion Phase. Those subjects who choose to continue in the OLE study (810P304) will have baseline procedures performed for that study; eligibility criteria will be confirmed (at Visit 1 of study protocol 810P304) or EOS (Visit 8) in this study (810P503).

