4.3.6 Early Termination

All subjects who discontinue early (i.e. during Titration period, Day 1 to Day 14) will be instructed to return to the study site for a final visit (EOS), one week after discontinuation. Subjects who discontinue from the study following Day 15 in the Titration period or during the Maintenance period will be offered a taper card and will return to the study site for a final visit (EOS).

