5.7 Completion of Study and Discontinuation of Subjects

Subjects will be considered to have completed the study if they complete all visits up to and including Visit 8. Any subject, who discontinues from the study during the Maintenance period or following day 15 in the Titration period, will be offered a taper kit, whereas subjects who

This document is confidential. It contains proprietary information of Supernus[®] Pharmaceuticals, Inc. Any viewing or disclosure of such information that is not authorized in writing by the Sponsor is strictly prohibited. Such information may be used solely for the purpose of reviewing or performing this study.

CONFIDENTIAL Version 3

discontinue prior Visit 4 (i.e. during Titration period, Day 1 to Day 14) will be instructed to return to the study site for a final visit, one week after discontinuation. All subjects who discontinue early will complete Visit 8, EOS procedures.

The Investigator(s) or subjects themselves may stop SM treatment at any time for safety or personal reasons. A subject is free to withdraw from the study at any time for any reason without prejudice to their future medical care by the physician or at the institution. The Investigator or Sponsor may also withdraw the subject at any time in the interest of subject safety. The withdrawal of a subject from the study should be discussed where possible and as applicable with the Medical Monitor, the Investigator and the Sponsor before the subject stops SM. Subjects removed from the study for any reason will not be replaced.

Reasons for withdrawal may include but are not limited to subject withdrawal of consent, occurrence of unmanageable AEs, or if it is in the best interest of the subject as per Investigator's discretion.

The primary reason for withdrawal must be recorded in the subject's medical record and on the eCRF. If a subject is withdrawn for more than one reason, each reason should be documented in the source document and the most medically significant reason should be entered on the eCRF.

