#### **Table 1 Schedule of Events and Assessments**

Phase	Pre-Tre	atment	Treatment			Conversion/Tap		
Period	Screening	Baseline	Titration		Maintenance			er
VISIT NUMBER	1	2	3	4	5	6	7	8 (EOS)
DAY	-45	-15	1	15	22	29	36	46
WINDOW (DAYS)	≤45d prior to Visit 3	≥15d prior to Visit 3	14d±2d from Visit 2	14d±2d from Visit 3	21d±2d from Visit 3	28d±2d from Visit 3	7d±2d from Visit 6	10d±1d from Visit 7
Informed Consent/Assent a	$X^b$							
R-MOAS Scale	X	X	X	X	X	X	X	X
MINI-KID & Vitiello Aggression Scales	X							
Medical History	X		X c					
Demographics	X							
Physical Examination & ECG (12-lead)	X						X	
Inclusion/Exclusion Criteria	X		$X^d$					
Randomization			$X^{b}$					
Urine Drug Screen	X	X	X	X	X	X	X	X
Pregnancy Test e	$X^{f}$	X	X	X	X	X	X	X
Diary Training & Distribution or Evaluation		X	$X^{g}$	X	X	X	X	
Vital Signs h	X		X	X	X	X	X	X
Weight, Height, BMI	X		X			X		X
Hematology/Chemistry/U rinalysis	X		X				X	X
PK Blood Sampling i					X	X		
PGx sampling 	X							

Version 2 Page **7** of **16 11/29/2023** 

a. Written consent must be obtained prior to performing any study-related procedure.

	1	1 0	<del>, ,</del>	1				
Columbia Suicide Severity Rating Scale (CSSRS)	X		X	X	X	X	X	X
Caregiver and Investigator CGI-S	$X^{j}$		X	X	X	X	X	
Caregiver and Investigator CGI-I				X	X	X	X	
SNAP-IV, CHQ-PF28, SIPA			X				X	
Infrequent Behaviors Checklist		X k	X	X	X	X	X	
Simpson-Angus, Barnes & AIMS			X	X	X	X	X	X
Adverse Events			X	X	X	X	X	X
Concomitant Medications	X	X	X	X	X	X	X	X
Drug Dispensation			X b	X	X	X	X	
Drug Return and Compliance				X	X	X	X	X
Diary Return				-				X

- b. Subject number will be assigned via
- c. Assess for any clinically significant change in Medical History since screening.
- d. Confirm inclusion/exclusion criteria.
- e. Urine pregnancy test will be performed for all female subjects. Prior to the administration of the first dose of SM subjects will have to be tested as negative to continue in the study. If Visit 1 and Visit 2 occur on the same day then both urine and serum pregnancy tests must be performed.
- f. Serum pregnancy test will be performed at Screening for all female subjects.
- g. Diary compliance must be at least 70% (minimum of 11 days out of 15) to qualify for randomization.
- h. Heart Rate (HR), blood pressure (BP), temperature, and respiratory rate will be measured.
- i. PK blood samples will be obtained over two visits

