# **7.3** Vital Signs

The absolute value and change from baseline to EOS for vital signs (body temperature, heart rate, respiration rate, systolic blood pressure, weight, height, BMI and diastolic blood pressure) will be summarized using descriptive statistics for continuous variables by treatment group as described in Section 5.1. The summary will be presented by treatment groups. Subject listings of Vital signs will be presented.

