#### **7.4** ECG

The absolute value and change from baseline to EOS for ECG parameters (heart rate, PR interval (msec), QRS interval (msec), QT interval (msec), and QT corrected for heart rate using Fridericia's (QTcF) correction formula, RR interval (msec)) will be summarized using descriptive statistics for continuous variable by treatment groups as described in Section 5.1. Subject listings of ECGs will be presented.

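### SAP 7.2 and 7.3 tabulate labs and vital signs by arm only at EOS (Visit 8), after conversion, taper or stopping, and SAP 7.4 asks for an EOS ECG that is not scheduled

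*SAP*

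**What the plan says.** SAP 7.2 (laboratory tests): "The absolute value and change from baseline to EOS for laboratory tests will be summarized using descriptive statistics", by treatment group and laboratory category. SAP 7.3: "The absolute value and change from baseline to EOS for vital signs", by treatment group. SAP 7.4: "The absolute value and change from baseline to EOS for ECG parameters", by treatment group. None of the three names another post-baseline visit for tabulation.

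The SAP does not define EOS in words, but its Table 1 attaches the label to Visit 8, Day 46. The protocol agrees:

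- Section 4.3.3 (conversion): "Subjects will return to the study site for a final end-of-study (EOS) visit, (Visit 8), after completing the Conversion Phase".
- Section 4.3.5: "Subjects will return to the study site for a final visit, after completing the 10 day period of Taper or Conversion Phase".
- Section 4.3.6, for those who stop during titration: they "will be instructed to return to the study site for a final visit (EOS), one week after discontinuation".
- Section 5.7: "All subjects who discontinue early will complete Visit 8, EOS procedures".

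Protocol 9.5.4, 9.5.5 and 9.5.6 planned laboratory, vital-sign and ECG summaries by visit and treatment group. For vital signs, change to the final visit was to be shown as well. Protocol 8.1 lets the SAP override these methods.

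**The concern.** A safety table by randomized arm is informative when the arms differ in what they are taking. At Visit 8 that no longer holds. Subjects entering the open-label study have been brought to 36 mg/day SPN-810 whichever arm they came from. Those who declined have been tapered, and those who left early have stopped. The one visit that SAP 7.2 and 7.3 name is therefore a visit at which the randomized contrast has been taken apart, while values from the end of randomized treatment are collected but not assigned to any table.

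SAP 5.1 limits the analysis after the halt to the primary endpoint, the key secondary endpoints and safety. The laboratory panel includes prolactin and metabolic parameters. As worded, the by-arm tables would not show how the arms compared on these at the end of randomized treatment, and a reader could take the Visit 8 table for that comparison. The ECG table has a simpler defect: nothing is scheduled at its timepoint.

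**Working it through.** **1. Timing of EOS.** Table 1 puts Visit 7 at Day 36 and Visit 8 at 10 ± 1 days after it. 36 + 10 = Day 46, which reproduces the stated EOS day. The gap is 9 to 11 days. Visit 6 is Day 29 ± 2 and Visit 7 is 7 ± 2 days later, so Visit 7 can fall at Day 36 ± 4 and Visit 8 at Day 46 ± 5, that is Day 41 to 51. Maintenance ends on Day 35, so the nominal EOS is 46 − 35 = 11 days after the last Maintenance day.

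**2. What is scheduled after baseline (SAP Table 1; protocol Table 1 and 5.3.4 to 5.3.8).**

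| Assessment | Post-baseline visits | Before conversion/taper | At Visit 8 |
|---|---|---|---|
| Hematology, chemistry, urinalysis | 7, 8 | 1 | 1 |
| Vital signs | 4, 5, 6, 7, 8 | 4 | 1 |
| Weight, height, BMI | 6, 8 | 1 | 1 |
| ECG | 7 | 1 | 0 |

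The row "Physical Examination & ECG (12-lead)" in Table 1 is marked at Visits 1 and 7 only, and the Visit 8 procedure list in protocol 5.3.8 has no ECG. SAP 5.7 allows no substitution for missing data, so a Visit 7 ECG cannot be moved into an EOS cell.

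**3. Exposure at EOS by arm and path.**

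| Path to EOS | SPN-810 arm | Placebo arm |
|---|---|---|
| Conversion | on SPN-810 | on SPN-810 (disagrees with arm) |
| Taper | off (disagrees with arm) | off |
| Early stop without taper | off (disagrees with arm) | off |

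2 arms × 3 paths = 6 groups. Arm and exposure disagree in 3 of 6, and among completers (first two rows) in 2 of 4. These count groups, not subjects.

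**4. Illustration, on assumed values only.** Set the between-arm effect at Visit 7 to 1. Let a share c of each arm convert and the rest taper. Let r be the part of the effect remaining after taper and f the part reached after conversion. The SPN-810 mean effect at Visit 8 is c + (1 − c)r and the placebo mean effect is c·f, so the difference is c(1 − f) + (1 − c)r.

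- r = 0, f = 1: difference 0 for every c.
- r = 0.25, f = 0.75: 0.25c + 0.25(1 − c) = 0.25.
- r = 0.5, f = 0.5: 0.5c + 0.5(1 − c) = 0.5.

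If the shares differ by arm (c₁ for SPN-810, c₀ for placebo) with r = 0 and f = 1, the difference is c₁ − c₀, which can take either sign. The documents give none of c, r or f.

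**5. Is a by-visit display implied elsewhere in the SAP?** SAP 6.2 asks for the CGI-S and R-MOAS by treatment group and visit, so the SAP says so where it means it. The sentence on by-visit displays in SAP 5.1 only sets a percentage denominator. SAP 5.1 explains why the list of outputs was shortened after the halt, but gives no reason for dropping the on-treatment visits from the outputs that were kept.

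**The case against.** The strongest reply is that EOS is used loosely. In SAP 7.4 it cannot literally be Visit 8, since no ECG is scheduled there. The protocol's abbreviation list expands it only as End of Study, and the spelled-out phrase sometimes refers to Visit 7: the secondary endpoints in protocol 6.2 are placed at Visit 7 by 9.2.1, and the final physical examination in 6.4.8 is at Visit 7 in Table 1. The author might have meant the end of treatment throughout.

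This shows that EOS needs a definition, but it does not rescue 7.2 and 7.3. Wherever the abbreviation is tied to a visit, that visit is Visit 8 or the early discontinuer's final visit. Reading it as the last available value still gives Visit 8 for completers' labs and vital signs.

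Other points stand in part:

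- Taper runs to Day 45 and Visit 8 is nominally Day 46, so some drug effect may persist. Coding tapered subjects as off is a simplification.
- Protocol 4.3.6 puts the final visit of titration-period discontinuers one week after stopping; 5.3.8 says within one week. Either way it follows stopping.
- For open-label entrants, the Synopsis moves adverse events starting after Visit 7 to the extension study's summaries. Neither document says the same of their Visit 8 labs and vital signs, so 7.2 and 7.3 as written include them.
- Unscheduled ECGs are allowed (protocol 6.4.9), so a few EOS ECGs may exist, but not as a planned dataset.
- The tables are descriptive, the study was halted, and listings keep all values. Protocol 9.5.5 also planned vital-sign change to the final visit, so that table is not new; the by-visit display beside it has gone.

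These limit the harm but do not change the finding.

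**Conclusion.** The concern holds. Followed as written, SAP 7.2 and 7.3 give by-arm laboratory and vital-sign tables at a visit where arm and SPN-810 exposure disagree in 3 of 6 arm-by-path groups, and SAP 7.4 gives an ECG table with 0 scheduled assessments at its timepoint against 1 at Visit 7. The effect on any particular parameter cannot be sized or signed, because the documents give neither the path shares nor the speed of onset and washout.

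The conclusion rests on reading EOS as Visit 8, as SAP Table 1 labels it, and on converters' Visit 8 data entering these tables. It should be fixed, but it is not critical: the summaries are descriptive, listings are complete, and the extrapyramidal, C-SSRS and special-interest adverse event outputs carry no EOS restriction.

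**What to change.** 1. Define EOS in the SAP.
2. In 7.2 and 7.3, summarize absolute value and change from baseline by visit and treatment group, as SAP 6.2 does. Name Visit 7 (Visit 6 for weight, height and BMI) as the end-of-randomized-treatment comparison.
3. Keep the Visit 8/EOS table, shown separately by arm and by conversion, taper or early stop. It holds the only scheduled post-baseline labs for subjects who leave before Visit 7, so it should not be replaced. If the groups are small, counts by path with the listings would be a workable minimum.
4. In 7.4, replace EOS with Visit 7; unscheduled ECGs remain in the listings.

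The cost is SAP wording and a few more descriptive tables. No new data are needed, and no subject drops out of the laboratory or vital-sign summaries. The change restores the by-visit displays that protocol 9.5.4 to 9.5.6 planned.
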